### 1.3 Secondary Objectives

1. To determine the toxicity of pembrolizumab in patients with recurrent high-grade meningioma (WHO grade II atypical meningioma and WHO grade III anaplastic meningioma)
2. To estimate the overall survival of patients with recurrent high-grade meningioma receiving pembrolizumab
3. To estimate the response rate of patients with recurrent high grade meningioma receiving pembrolizumab

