#### 11.2 Definitions

Evaluable for objective response. Only those participants who have measurable CNS disease present at baseline, have received at least one cycle of therapy, and have had their disease re-evaluated will be considered evaluable for target disease response. These participants will have their response classified according to the definitions stated below. (Note: Participants who exhibit objective disease progression prior to the end of cycle 1 will also be considered evaluable.)

Evaluable non-measurable evaluable disease. Participants who have lesions present at baseline that are evaluable but do not meet the definitions of measurable disease, have received at least one cycle of therapy, and have had their disease re-evaluated will be considered evaluable for non-target disease. The response assessment is based on the presence, absence, or unequivocal progression of the lesions.

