### 11.3 Response Criteria

#### 11.3.1.1 Evaluation of Intracranial Lesions

Complete Response (CR): Requires all of the following:

- complete disappearance of all enhancing measurable and nonmeasurable disease sustained for at least 4 weeks
- no new lesions
- stable or decreasing corticosteroids (the steroid dose at the time of the scan evaluation should be no greater than the dose at time of baseline scan)
- stable or improved clinically

*Participants with non-measurable disease cannot have a complete response. The best possible response is stable disease.*

Partial Response (PR): All of the following criteria must be met:

- Greater than or equal to 50% decrease compared to baseline in the sum of products of perpendicular diameters of all measurable enhancing lesions sustained for at least 4 weeks. In the absence of a confirming scan 4 weeks later, this scan will be considered only stable disease.
- no progression of non-measurable disease.
- no new lesions
- stable or reduced corticosteroid dose (the steroid dose at the time of the scan evaluation should be no greater than the dose at time of baseline scan)
- stable or improved clinically

Progressive Disease (PD): At least one of the following must be true:

- $\geq 25\%$  increase in the sum of products of all measurable lesions over smallest sum observed (over baseline if no decrease) using the same techniques as baseline
- clear worsening of any nonmeasurable disease\*
- appearance of any new enhancing lesion/site
- clear clinical worsening (unless clearly unrelated to this cancer, e.g. seizures, medication side effects, complications of therapy, cerebrovascular events, infection)
- failure to return for evaluation due to death or deteriorating condition

\* Progression of non-measurable CNS lesions is defined as follows:

- a lesion initially at baseline  $\leq 5$ mm in diameter that increases to  $\geq 10$ mm in diameter, or
- a lesion initially at baseline 6-9 mm in diameter that increases by at least 5 mm in diameter.
- a lesion that is smaller than 10mm that is too complex or has poorly defined margins, that is now unequivocally progressing by more than 25%

Stable Disease (SD): All of the following criteria must be met:

- Does not qualify for CR, PR or progression
- All measurable and non-measurable sites must be assessed using the same techniques as baseline
- Stable clinically.

A summary of the response criteria is in the below:

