### 11.3.2 Duration of Response

Duration of overall response: The duration of overall response is measured from the time measurement criteria are met for CR or PR (whichever is first recorded) until the first date that recurrent or progressive disease is objectively documented (taking as reference for progressive disease the smallest measurements recorded since the treatment started, or death due to any cause. Participants without events reported are censored at the last disease evaluation).

Duration of overall complete response: The duration of overall CR is measured from the time measurement criteria are first met for CR until the first date that progressive disease is objectively documented, or death due to any cause. Participants without events reported are censored at the last disease evaluation.

Duration of stable disease: Stable disease is measured from the start of the treatment until the criteria for progression are met, taking as reference the smallest measurements recorded since the treatment started, including the baseline measurements.

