### 11.4 **Antitumor Effect – Extracranial lesion assessments**

For patients that have metastatic meningioma, participants should be re-evaluated for extracranial response every 6 weeks. In addition to a baseline scan, confirmatory scans should also be obtained 6 weeks following initial documentation of objective response.

Response and progression will be evaluated in this study using the new international criteria proposed by the Response Evaluation Criteria in Solid Tumors (RECIST) guideline (version 1.1) [*Eur J Ca* 45:228-247, 2009]. Changes in the largest diameter (unidimensional measurement) of the tumor lesions and the shortest diameter in the case of malignant lymph nodes are used in the RECIST criteria.

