#### **Secondary Endpoints:**

1. Toxicity by CTCAE criteria (grade 3 or higher hematologic toxicity; grade 3 or higher neurologic toxicity)
2. Overall survival
3. Intracranial response as defined by RANO criteria

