### **13.7 Analysis of Secondary Endpoints**

Safety and Tolerability: All adverse events recorded during the trial will be summarized for all patients having received one or more doses of pembrolizumab. The proportions of patients with grade-3 or higher hematologic toxicities or grade-3 or higher neurologic toxicities will be presented with 90% exact binomial confidence intervals. The incidence of events that are new or worsening from the time of first dose of treatment will be summarized according to system organ class and/or preferred term, severity (based on CTCAE grade), type of adverse event, and relation to study treatment. Deaths reportable as SAEs and non-fatal serious adverse events will be listed by patient and tabulated by primary system organ class, and type of adverse event.

Overall Survival: The distributions of overall survival will be summarized using the method of Kaplan-Meier. The follow-up of patients who are alive at the time of analysis will be censored at the date of last assessment of vital status. Median OS will be presented and accompanied by 90% confidence intervals estimated using log(-log(survival)) methodology. Survival point estimates at 3 and 6 months will also be presented with confidence intervals.

Intracranial/Extracranial Response: Contrast-enhanced cranial magnetic resonance imaging (MRI) will be performed every 6 weeks. The proportion of patients with intracranial response (CR, PR or SD by RANO) will be presented with a two-sided, 90% exact binomial confidence interval.

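### Section 13.7 counts stable disease as intracranial response, so the plan reports disease control under that name and includes no CR+PR rate for secondary objective 3

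*Combined protocol and SAP*

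**What the plan says.** Section 1.3 sets the third secondary objective: "To estimate the response rate of patients with recurrent high grade meningioma receiving pembrolizumab". Section 13.2 lists the matching endpoint as "Intracranial response as defined by RANO criteria", without saying which RANO categories count.

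Section 13.7 is the only place that does: "The proportion of patients with intracranial response (CR, PR or SD by RANO) will be presented". The accompanying interval is exact binomial, two-sided, at 90%.

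Section 11 treats SD as something other than response. In 11.3.1.1 the first condition for SD is "Does not qualify for CR, PR or progression", and a PR that lacks a confirming scan is counted down to SD. Section 11.3.2 states: "The duration of overall response is measured from the time measurement criteria are met for CR or PR". It defines duration of stable disease separately. Section 2.1, reviewing earlier systemic therapy for recurrent meningioma, reports a response rate of zero in almost every study.

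**The concern.** A reader who meets a response rate in an oncology report, or in this protocol's own background section, takes it to mean tumour shrinkage that qualifies as CR or PR. Section 13.7 attaches the name to a quantity that also counts patients whose tumours did not change enough to be classified. Followed as written, the plan could produce a substantial response figure from a trial in which no tumour responded. That figure could not be compared with the historical rate in Section 2.1. The quantity a reader would expect under objective 3 would not be among the planned outputs.

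**Working it through.** **1. The plan's own figures.** No expected rate, precision or power is given for response, so there is nothing to reproduce for this endpoint. The primary rule in 13.6 was checked to confirm that it stands apart. With X ~ Binomial(24, p) and success at X ≥ 10:
- P(X ≥ 10 | p = 0.26) = 0.069, within the one-sided 0.1.
- P(X ≥ 10 | p = 0.52) = 0.888, matching the stated power of at least 88%.

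Response does not enter this rule.

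**2. Passages side by side.**

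| Place | Treatment of SD |
|---|---|
| 11.3.1.1, SD | A category exclusive of CR and PR |
| 11.3.1.1, PR | An unconfirmed PR is downgraded to SD; the downgrade would not alter a proportion that also counts SD |
| 11.3.2 | Response duration starts at CR or PR; SD duration is separate |
| 2.1 with 13.6 | Historical response near zero, historical PFS6 26% |
| 13.7 | SD counted as response |

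On the fourth row, patients who are progression-free at six months without CR or PR have SD. A near-zero response rate beside a 26% PFS6 therefore makes sense only if response excludes SD. The populations differ (all grades in 2.1, grade II/III in 13.6), so this is supporting evidence rather than proof.

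**3. Size, by illustration.** The documents give no CR, PR or SD rates, so the counts are assumed. The denominator of 24 is also assumed: it is the PFS6 evaluable number in 13.3 and 13.6. The Clopper-Pearson 90% limits for x of n are:
- lower = 0.05 quantile of Beta(x, n − x + 1), or 0 if x = 0
- upper = 0.95 quantile of Beta(x + 1, n − x)

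For x = 0 and n = 24 the upper limit is 1 − 0.05^(1/24) = 0.117.

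| Assumed CR+PR | Assumed SD | Reported under 13.7 | CR+PR rate |
|---|---|---|---|
| 0 | 6 | 25% (11.5 to 43.5%) | 0% (0 to 11.7%) |
| 0 | 12 | 50% (31.9 to 68.1%) | 0% (0 to 11.7%) |
| 0 | 18 | 75% (56.5 to 88.5%) | 0% (0 to 11.7%) |

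With 12 or 18 SD the two intervals do not overlap. With 6 they only just touch.

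**4. What follows once response means CR+PR.** Section 11.3.1.1 requires a PR to be sustained for four weeks and otherwise treats it as SD. Section 11.3.1.2 keeps a response that has gone by the next scheduled MRI on record as a non-sustained response. Suppose there are 2 such PRs among 24 and no other CR or PR. The rate is 0/24 = 0% (0 to 11.7%) under the first rule and 2/24 = 8.3% (1.5 to 24.0%) if non-sustained responses count. Under the pooled definition both patients count either way, so the conflict is hidden at present.

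**The case against.** The strongest reply is that 13.7 defines its term openly. Neither the objective nor the endpoint list says that response means CR+PR, and Section 11 sometimes uses the word for any category, naming SD as the best response available to patients without measurable disease. Best response is also assigned per patient, so CR+PR can be derived later without new data. Some of this stands. A reader might infer that objective 3 has no planned analysis at all, which goes too far: 13.7 does plan a statistic under that name. What is missing is the CR+PR proportion, and what is wrong is that the definition conflicts with 11.3.1.1 and 11.3.2. The loose usage in Section 11 is a label for categories and does not set a criterion for a rate. That a figure can be derived does not make it planned. Nor does the parenthesis in 13.7 read as a list of separate outputs, since it describes one proportion with one interval.

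Three further inferences are tempting and not supported.
- **The denominator is undefined.** Section 11.2 does say who is evaluable for objective response: "Only those participants who have measurable CNS disease present at baseline, have received at least one cycle of therapy", and with disease re-evaluated (objective progression before the end of cycle 1 also qualifies). What is lacking is a reference to that set in 13.7.
- **A listed extracranial analysis is missing.** The heading in 13.7 is "Intracranial/Extracranial Response", and Section 11.4 says "participants should be re-evaluated for extracranial response every 6 weeks". But that applies to patients with metastatic meningioma, described in the study calendar notes as rare, and the listed endpoint is intracranial only. The heading needs clarifying, no more.
- **The response figure can only fall once redefined.** This is true only for a fixed denominator. With 3 CR/PR and no SD (assumed), moving from 26 patients to 24 raises the figure from 3/26 = 11.5% to 3/24 = 12.5%.

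**Conclusion.** The point holds as an inconsistency of definition with a reporting consequence. Section 13.7 labels disease control as intracranial response, against the protocol's own usage, and no CR+PR proportion is planned for secondary objective 3. The possible distortion is large: 50% against 0% in the middle illustration. That size rests on assumed counts and on borrowing the PFS6 denominator of 24. The response-evaluable set in 11.2 has different conditions and may be smaller. The conflict over a PR that is not sustained is real, but it affects a reported rate only after response is redefined.

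A reader might infer that the trial's main conclusion is at risk. The documents do not support that. Response is a descriptive secondary endpoint with no test, decision rule or sample size attached, and the rule of at least 10 of 24 for PFS6 is untouched.

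**What to change.** In Section 13.7:
- Define the intracranial response rate as CR+PR by RANO, with a two-sided 90% exact binomial interval.
- State the denominator, for example the set evaluable for objective response in 11.2.
- Report CR+PR+SD as a separate line named disease control rate.

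As a consequence, reconcile 11.3.1.1 with 11.3.1.2 so that a PR that is not sustained is counted one way.

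The cost is a few wording edits. No new data are needed, because best response is already assigned per patient and all brain MRI scans are centrally reviewed (11.3.4). The downside is that, for a given denominator, the reported response figure can only stay the same or fall. If the denominator changes too, this need not hold.

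Two minor clarifications can be made separately. The 13.7 heading should say whether extracranial response is included, reported separately or not analysed. Sections 9.3.3, 9.3.5.3 and 13.8 should name the responder definition they use; 13.8 also calls response the primary endpoint, which under 13.2 is PFS6.

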**3.1.5 Age  $\geq$  18 years**

**3.1.6 ECOG Performance Status  $\leq$  2**

**3.1.7 Patient history:** Patients with history of NF may have other stable CNS tumors (schwannoma, acoustic neuroma or ependymoma) if lesions have been stable for 6 months.

**3.1.8** Metastatic meningiomas (as defined by extracranial meningiomas) and meningioma with extra-cranial spread are allowed.

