#### For Participants with Measurable Disease (i.e., Target Disease)

Target Lesions	Non-Target Lesions	New Lesions	Overall Response	Best Overall Response when Confirmation is Required*
CR	CR	No	CR	≥4 wks Confirmation**
CR	Non-CR/Non-PD	No	PR	≥4 wks Confirmation**
CR	Not evaluated	No	PR	
PR	Non-CR/Non-PD/not evaluated	No	PR	
SD	Non-CR/Non-PD/not evaluated	No	SD	Documented at least once ≥4 wks from baseline**
PD	Any	Yes or No	PD	no prior SD, PR or CR
Any	PD***	Yes or No	PD	
Any	Any	Yes	PD	

* See RECIST 1.1 manuscript for further details on what is evidence of a new lesion.            ** Only for non-randomized trials with response as primary endpoint.            *** In exceptional circumstances, unequivocal progression in non-target lesions may be accepted as disease progression.
 
Note: Participants with a global deterioration of health status requiring discontinuation of treatment without objective evidence of disease progression at that time should be reported as “symptomatic deterioration.” Every effort should be made to document the objective progression even after discontinuation of treatment.
				

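### Secondary objective 3 asks for a response rate of patients, but only intracranial response is analysed, and the centrally read RECIST data go unused

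*Combined protocol and SAP*

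**What the plan says.** **Objective and endpoint.** The third secondary objective in Section 1.3 is "To estimate the response rate of patients with recurrent high grade meningioma receiving pembrolizumab". It names no compartment. The matching entry in the Section 13.2 endpoint list is narrower: "Intracranial response as defined by RANO criteria".

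**Analysis.** The paragraph in Section 13.7 is headed "Intracranial/Extracranial Response". The one statistic under it is: "The proportion of patients with intracranial response (CR, PR or SD by RANO) will be presented", with a two-sided 90% exact interval. Stable disease therefore counts as response. The paragraph states no denominator.

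**Who can enter.** Section 3.1.1 accepts intracranial or metastatic disease, and Section 3.1.8 says: "Metastatic meningiomas (as defined by extracranial meningiomas) and meningioma with extra-cranial spread are allowed". Neither requires an intracranial lesion as well.

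**What is collected outside the CNS.** Section 11.4 says: "For patients that have metastatic meningioma, participants should be re-evaluated for extracranial response every 6 weeks". It adopts RECIST 1.1 and gives rules for target lesions, non-target lesions, best overall response and duration. Section 11.4.7 sends all non-CNS scans to central review. No section analyses the RECIST result or combines it with the RANO result.

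**The concern.** The objective and the 13.7 heading promise more than the analysis delivers. With two compartments assessed by two sets of criteria, a response rate of patients needs a rule that joins them, and there is none. Two kinds of patient are affected.

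- **Progression outside the CNS with intracranial CR, PR or SD.** The patient counts in the reported proportion. The same patient is a PFS event under Section 11.4.6 and falls under removal for progression in Section 12.1.2. The report would show the intracranial success without an overall rate to set against it.
- **Extracranial disease only.** The patient has a RECIST response but no part in the analysed endpoint, so a true extracranial response would not reach objective 3. Section 2.1 says that response rates have been 0% in nearly all studies of systemic therapy in recurrent disease, so a single response would be informative.

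If no rule is written in advance, someone must choose one after the results of an open-label, single-arm trial are known.

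**Working it through.** **The plan's own figures.** No sample size or precision is stated for response. The only design figure is for 6-month PFS in Section 13.6: at least 10 of 24, 26% against 52%, one-sided level 0.1, power at least 88%. Exact binomial tails give P(X ≥ 10 | n = 24, p = 0.52) = 0.888 and P(X ≥ 10 | n = 24, p = 0.26) = 0.069. The stated power is reproduced, and nothing below changes it.

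**Step 1: can extracranial progression count as intracranial response?** The progression criteria in Section 11.3.1.1 are for intracranial lesions. RECIST progression in the body would turn the intracranial result into progression only if it caused clear clinical worsening, or if the new-lesion criterion, which mentions a new enhancing lesion or site, were read to cover the body. The text does not give that second reading. Section 13.9.2 deals with systemic progression for the primary objective only. So clinically silent extracranial progression leaves the patient in the numerator.

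**Step 2: where does an extracranial-only patient go?** Three readings are possible.

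- Section 11.2 limits evaluability for objective response to patients with measurable CNS disease at baseline, so the patient is excluded.
- Section 13.7 speaks only of the proportion of patients, without citing 11.2. Read literally, the patient stays in the denominator as a non-responder.
- Section 11.3.1.2 lets participants without measurable disease reach SD or PD. A patient entered as SD counts as a response.

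Section 11.2 makes the first reading the most natural, but 13.7 does not say so.

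**Step 3: size on the planned statistic (CR, PR or SD).** Inputs: n = 24 evaluable (Section 13.6). Assumed, because the documents give neither figure: 12 patients with intracranial CR, PR or SD, and 1 to 3 affected patients. Intervals are two-sided 90% Clopper-Pearson. Each patient moves the proportion by 1/24 = 4.2 points.

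| Counted patients with extracranial PD | Proportion once they are removed | 90% CI |
|---|---|---|
| 0 | 12/24 = 50.0% | 31.9–68.1 |
| 1 | 11/24 = 45.8% | 28.2–64.2 |
| 2 | 10/24 = 41.7% | 24.6–60.3 |
| 3 | 9/24 = 37.5% | 21.2–56.3 |

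Separately, suppose that 1 to 3 of the other 12 patients have extracranial disease only:

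| Handling | 1 patient | 2 patients | 3 patients |
|---|---|---|---|
| Non-responder | 12/24 = 50.0% | 12/24 = 50.0% | 12/24 = 50.0% |
| Excluded | 12/23 = 52.2% | 12/22 = 54.5% | 12/21 = 57.1% |
| Entered as SD | 13/24 = 54.2% | 14/24 = 58.3% | 15/24 = 62.5% |

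**Step 4: confirmation, set side by side.**

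- *Intracranial.* Section 11.3.1.1 treats a PR without a confirming scan as stable disease. Section 11.3.1.2 still records a response that does not persist, marked as non-sustained.
- *Extracranial.* Section 11.4 asks for confirmatory scans, and Section 11.4.4.4 makes best response depend on confirmation. A footnote to the table that follows limits the confirmation entries: "Only for non-randomized trials with response as primary endpoint". In this trial the primary endpoint is 6-month PFS, so the footnote switches them off.

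On the planned proportion an unconfirmed intracranial PR counts either way, as PR or as SD. The conflict starts to matter once a CR or PR rate is reported.

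**The case against.** The strongest reply is that nothing was left out. Section 13.2 names intracranial RANO response as the endpoint, Section 13.7 analyses exactly that, and a compartment-specific endpoint by design does not score the other compartment. On this view there is only a mismatch of wording, which could be cured by narrowing the objective and the heading. The first part stands: a reader might infer that 13.7 departs from its own endpoint, and it does not. Narrowing the wording would be consistent, but it would leave the RECIST data collected and centrally read to no analytic purpose.

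Three stronger readings are also tempting, and the documents do not support them.

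- *That extracranial-only patients cannot be scored, or must sit in the intracranial denominator.* Section 11.4.4 scores them, and Section 11.2 points to leaving them out of the intracranial set. What is missing is a use for the score and an explicit link from 13.7 to 11.2.
- *That the trial's conclusion about benefit is inflated.* The decision rests on 6-month PFS. Section 11.4.6 counts progression or death without limit to a compartment, and Section 13.9.2 keeps patients with early systemic progression in the analysis.
- *That deleting the table footnote would put both compartments on one confirmation standard.* The two intracranial sections would still disagree.

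It is also fair to say that the intervals in Step 3 overlap heavily and that the endpoint carries no test or threshold.

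**Conclusion.** The gap is real and limited. As written, the plan reports intracranial disease control and does not deliver the response rate of patients that objective 3 asks for. Extracranial progression can coexist with a counted response, and an extracranial response is never reported.

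The size is 4.2 points per affected patient, on one descriptive secondary proportion. The base of 12/24 and the count of 1 to 3 are assumptions. Footnote u to the Section 10 calendar calls extracranial metastases rare, so the true count may be zero. The primary endpoint, its cut-off of 10 of 24 and its power do not change. The case for acting is that the remedy costs little and lets the trial answer a stated objective, not that the main result is at risk.

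**What to change.** 1. **Sections 13.2 and 13.7: add a patient-level overall response.** Report the proportion with CR or PR, with a two-sided 90% exact interval. Progression in either compartment is progression overall, and patients with extracranial disease only are scored by RECIST. State the denominator. Leaving SD out is deliberate, since objective 3 asks for a response rate.
2. **Section 13.7: keep the planned intracranial CR, PR or SD proportion.** Label it as intracranial disease control, and tie its denominator expressly to the evaluability rule in Section 11.2.
3. **Sections 1.3, 13.2 and 13.7: align the wording** so that the objective, the endpoint list and the heading describe the same two quantities.
4. **Reconcile confirmation** across Sections 11.3.1.1, 11.3.1.2, 11.4, 11.4.4.4 and the table footnote, so that one stated standard applies in both compartments.

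The cost is a few lines of text and one extra reported proportion. No additional scans, visits or patients are needed, because the images are already scheduled and centrally read.
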